Inclusion criteria: (1) meet the 2018 edition of ADA Diabetes Medical Diagnosis and Treatment Criteria and diagnosed with T2DM; (2) patients using insulin or sulfonylureas; (3) disease duration ≥ 1 year, age ≥ 18 years; (4) history of hypoglycemia occurrence in the past 6 months; (5)

patients with a tendency of avoidance and compromise in T2DM Hypoglycemic Coping Styles Inventory; (6) good communication and verbal skills; (7) have a smartphone and know how to use it; and (8) voluntarily participate in this study. Exclusion Criteria: (1) patients with type 1 diabetes mellitus; (2) patients with severe complications in combination with T2DM; and (3) patients who are participating in studies on other topics.

7. Intervention process

From August 2023 to January 2024, T2DM patients who met the inclusion and exclusion criteria were selected from 1 tertiary hospital in Chuzhou City. The control group implemented conventional diabetes health education, and the intervention group implemented health education based on IMB theory on the basis of the control group.

8. Sample size estimation

In this study, a randomized controlled trial was conducted to investigate the effect of intervention based on IMB model on the hypoglycemic coping style of T2DM patients, which was randomly divided into the control group and the intervention group, and the main observation index was the hypoglycemic coping style after the intervention. According to previous studies in similar literature, the control group was 30.14 ± 5.08 , and the intervention group was 34.40 ± 5.36 , with $\alpha = 0.05$, power = 0.95, and 1:1 parallel control. According to the formula for calculating the sample size of the mean value of the two groups, the sample size of the two groups was calculated to be 41 cases in each group, and at least 50 cases should be included in each group at the baseline, taking into account the 15% dropout rate, which made the total number of cases to be 100 in total.

9. Randomisation

Participants were identified through screening of medical records and face-to-face interviews, and participants signed a written consent form to participate in the study. After the baseline assessment, participants were randomly assigned to either the intervention or control group using a lottery method after drawing a labelled card in an opaque sealed envelope from an independent research assistant who was not involved in the recruitment and implementation of the study.

10. Measurement index

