General information questionnaire: day 1 of admission; Hypoglycemia Coping Styles Scale for Patients with Type 2 Diabetes Mellitus (primary indicator): day 1 of admission, 4 weeks post-intervention, 8 weeks post-intervention, and 12 weeks post-intervention; Fear of Hypoglycemia Scale Score (secondary indicator): day 1 of admission, 4 weeks post-intervention, 8 weeks post-intervention, and 12 weeks post-intervention; Health Information Acquisition Behavior Scale (secondary indicator): day 1 of admission, 4 weeks post-intervention Day 1, 4 weeks post-intervention, 8 weeks post-intervention, 12 weeks post-intervention; Type 2 Diabetes Knowledge Scale (secondary indicator). Day 1 of admission, 4 weeks post-intervention, 8 weeks post-intervention, and 12 weeks post-intervention.

11. Ethical consideration

The study was ethically approved by the Ethics Committee of the College of Nursing of Yangzhou University (YZUHL20220047).

12. Statistical analysis of data

SPSS 26.0 software was applied for data analysis. Describing the general demographic characteristics of the study population: Mean \pm standard deviation ($\pm s$) was used to describe measures that conformed to normal distribution, and median and interquartile spacing M (QR) were used to describe skewed distribution; count data were expressed as frequencies and constitutive ratios. Homogeneity test: the chi-square test or Fisher's

exact test was used for the count data of the two groups at baseline, non-parametric test was used for the rank count data, and t-test or non-parametric test was used for the measurement data. Repeated measures ANOVA was used to analyse the intervention effect of each indicator within groups, and two independent samples t-test was used to compare between groups at different time points before and after the intervention. The significance level $P < 0.05$ indicated that the difference was statistically significant.

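### Between-group differences at 4, 8 and 12 weeks are tested without adjusting for the day-1 score, so valid tests give up precision that the collected data could supply

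*Combined protocol and SAP*

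**What the plan says.** Section 10 (Measurement index) schedules the primary coping-styles scale at "day 1 of admission, 4 weeks post-intervention, 8 weeks post-intervention, and 12 weeks post-intervention". The three secondary scales follow the same schedule, although the entry for the health information scale is partly duplicated.

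Section 9 (Randomisation) fixes the order of events: "After the baseline assessment, participants were randomly assigned to either the intervention or control group using a lottery method". The day-1 scores therefore precede allocation.

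Section 12 (Statistical analysis of data) uses the scores in three ways:

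- Baseline homogeneity tests, in which "non-parametric test was used for the rank count data, and t-test or non-parametric test was used for the measurement data".
- A within-arm analysis: "Repeated measures ANOVA was used to analyse the intervention effect of each indicator within groups".
- The comparison of the arms: "two independent samples t-test was used to compare between groups at different time points before and after the intervention".

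No ANCOVA, change-score comparison or mixed model with baseline is named.

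**The concern.** A pre-randomisation score on the same scale is often among the better predictors of the follow-up score. Here it is collected for all four scales and then left out of the group comparison. A baseline homogeneity test describes imbalance but does not correct for it. A within-group ANOVA does not estimate a difference between arms.

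Two things are at stake. First, the uncertainty around each group difference is larger than it needs to be. That matters in a pilot whose stated purpose (section 5) includes initial effectiveness, because the estimate and its interval are what a later trial would draw on. Second, whatever chance baseline gap occurs in this one trial carries through to the unadjusted estimate in proportion to the baseline–follow-up correlation. The plan tests for such gaps but does not say what follows if one is found, which leaves room to choose an analysis after seeing the data.

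**Working it through.** **Inputs from section 8.** Control 30.14 ± 5.08; intervention 34.40 ± 5.36; α = 0.05; power 0.95; 1:1 allocation; 41 per arm before dropout; 15% dropout; at least 50 per arm enrolled.

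**Assumed.** The correlation r between day-1 and follow-up score is not in the documents, so 0.3, 0.5 and 0.7 are shown. Where baseline gaps are expressed in points, the baseline SD is taken as equal to the follow-up SD. The tests are two-sided.

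**1. The plan's own figure.** Difference = 34.40 − 30.14 = 4.26. Pooled SD = √((5.08² + 5.36²)/2) = 5.22. The normal approximation gives n = 2 × (5.22 × (1.960 + 1.645)/4.26)² = 39.05, so 40 per arm. The exact two-sided t-test calculation gives 41, as stated (power 0.954). Then 41/0.85 = 48.2, so 49, which the plan rounds up to 50. The trial is correctly sized for an unadjusted comparison of follow-up means.

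**2. Precision of the planned t-test.** Completers = 50 × 0.85 = 42.5, taken as 42 per arm. SE = 5.22 × √(2/42) = 1.140. Half-width of the 95% CI = t(0.975, 82 df) × SE = 1.989 × 1.140 = 2.27 points.

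**3. Precision with ANCOVA.** SE = 1.140 × √(1 − r²) × √(1 + 1/80). The last factor allows for average chance imbalance in the covariate. The t quantile has 81 df.

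| r | Half-width, points | Power at 4.26 points | Power at 2.13 points |
|---|---|---|---|
| unadjusted t-test | 2.27 | 0.959 | 0.46 |
| 0.3 | 2.18 | 0.970 | 0.49 |
| 0.5 | 1.98 | 0.989 | 0.56 |
| 0.7 | 1.63 | 0.999 | 0.73 |

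Power is from the noncentral t distribution with the same SEs; 2.13 points is half the planned effect. At r = 0.2 the half-width is 2.24. At r = 0.1 it is 2.27, the same as the t-test.

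**4. Validity of both methods.** In a simulation with 42 per arm and 40,000 runs for each r, type I error was 0.047 to 0.050 for the t-test and 0.049 to 0.050 for ANCOVA. Mean half-widths were 2.26 for the t-test and 2.17, 1.97 and 1.62 for ANCOVA. A separate simulation with 41 per arm found neither estimator biased, with ANCOVA variance 0.92, 0.76 and 0.53 of the t-test's.

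**5. Chance baseline gaps.** In SD units the difference between arm means at baseline has standard deviation √(2/n), which is 0.200 with 50 per arm and 0.218 with 42.

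| Gap, either direction | 50 per arm | 42 per arm |
|---|---|---|
| above 0.2 SD (about 1.0 point) | 32% | 36% |
| above 0.5 SD | 1.2% | 2.2% |

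Given a gap, the unadjusted estimate is expected to move by r × gap. A 1.0-point gap moves it by 0.3, 0.5 or 0.7 points, which is 7%, 12% or 16% of 4.26.

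**The case against.** The strongest reply is that nothing here is wrong. The t-test is valid, the sample size was calculated for exactly that test and reproduces, and at the planned effect the power is already about 0.96. That is correct, and the point is one of efficiency only.

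The gain also depends entirely on an unknown r. Inclusion criterion (5) admits "patients with a tendency of avoidance and compromise in T2DM Hypoglycemic Coping Styles Inventory", which may narrow the baseline range and lower r for the primary scale. At r = 0.3 the half-width falls by less than 0.1 point. This stands: the benefit for the primary outcome could be small. The three secondary scales are not used for selection, so the restriction does not act on them directly, but no SDs are given for them and no size can be attached.

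The SD of 5.22 comes from earlier literature, and the plan does not say whether it describes a total or a subscale score. That also stands. It affects the figures in points, but not the proportional narrowing for a given r.

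The plan promises P values rather than confidence intervals. The half-width is used here to express precision; the power columns show the same loss on the plan's own terms.

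Finally, the repeated measures ANOVA might have been meant as a group-by-time model. The text assigns it to within-group effects, and even a group-by-time test would not be a baseline-adjusted difference at each visit. This lowers certainty about intent without removing the gap.

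**Conclusion.** The point holds as a loss of precision, not as bias or an inflated error rate. With SD 5.22 and 42 completers per arm, baseline adjustment would shorten the interval by about 4% at r = 0.3 (2.18/2.27), 13% at r = 0.5 (1.98/2.27) and 28% at r = 0.7 (1.63/2.27). If the true effect is 4.26 points, the conclusion would seldom change. The gain matters more for the interval the pilot reports and for smaller effects.

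The range rests on an assumed r, and the low end is plausible for the primary scale. Validity here means each t-test taken singly with complete data; repeated testing over time points and scales, and missing data, are separate matters. The change is worth making because it costs almost nothing.

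**What to change.** In section 12, keep the baseline comparison as description and replace the follow-up between-group t-tests with:

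> For each scale, the between-group difference at 4, 8 and 12 weeks is estimated by ANCOVA with group as factor and the day-1 score of the same scale as covariate, and reported as an adjusted mean difference with 95% CI. The unadjusted two-sample t-test is reported as a sensitivity analysis.

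For the primary scale, state which score (total or subscale) is analysed, so that the covariate is defined. A mixed model for repeated measures with the day-1 score as covariate would serve equally well, provided it is specified in advance.

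The cost is a change of wording and one degree of freedom, with no new data. The 41 per arm remains valid and becomes slightly conservative if r is about 0.2 or more. If r is near 0.1 or below there is no gain, and the loss is negligible (half-width 2.27 either way at r = 0.1).
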